Immune-mediated peripheral neuromotor syndromes, such as Guillain-Barre and Myasthenia Gravis		Any Grade	
 The prompt diagnosis of immune-mediated peripheral neuromotor syndromes is important, since certain patients may unpredictably experience acute decompensations which can result in substantial morbidity or in the worst case, death. Special care should be taken for certain sentinel symptoms which may predict a more severe outcome, such as prominent dysphagia, rapidly progressive weakness, and signs of respiratory insufficiency or autonomic instability Patients should be evaluated to rule out any alternative etiology (e.g., disease progression, infections, metabolic syndromes and medications, etc.). It should be noted that the diagnosis of immune-mediated peripheral neuromotor syndromes can be particularly challenging in patients with underlying cancer, due to the multiple potential confounding effects of cancer (and its treatments) throughout the neuraxis. Given the importance of prompt and accurate diagnosis, it is essential to have a low threshold to obtain a neurological consult Neurophysiologic diagnostic testing (e.g., electromyogram and nerve conduction investigations, and “repetitive stimulation” if myasthenia is suspected) are routinely indicated upon suspicion of such conditions and may be best facilitated by means of a neurology consultation 
Important to consider that the use of steroids as the primary treatment of Guillain-Barre is not typically considered effective. Patients requiring treatment should be started with IVIG and followed by plasmapheresis if

Dosing Modification and Toxicity Management Guidelines for Immune-mediated, Infusion Related, and Non Immune-mediated Reactions (MEDI4736 Monotherapy or Combination therapy with Tremelimumab or Tremelimumab monotherapy)

	Grade of the Event (NCI CTCAE version 4.03)	Dose Modifications	Toxicity Management
			not responsive to IVIG
	Grade 1	No dose modification	
 - Discuss with the study physician - Care should be taken to monitor patients for sentinel symptoms of a potential decompensation as described above - Obtain a neurology consult unless the symptoms are very minor and stable
	Grade 2	Hold study drug/study regimen dose until resolution to \leq Grade 1 Permanently discontinue study drug/study regimen if it does not resolve to \leq Grade 1 within 30 days or if there are signs of respiratory insufficiency or autonomic instability	Grade 2 
 - Discuss with the study physician - Care should be taken to monitor patients for sentinel symptoms of a potential decompensation as described above - Obtain a Neurology Consult - Sensory neuropathy/neuropathic pain may be managed by appropriate medications (e.g., gabapentin, duloxetine, etc.) 
MYASTHENIA GRAVIS
 
 o Steroids may be successfully used to treat Myasthenia Gravis. Important to consider that steroid therapy (especially with high doses) may result in transient worsening of myasthenia and should typically be administered in a monitored setting under supervision of a consulting neurologist. o Patients unable to tolerate steroids may be candidates for treatment with plasmapheresis or IVIG. Such decisions are best made in consultation with a neurologist, taking into account the unique needs of each patient. o If Myasthenia Gravis-like neurotoxicity present, consider starting acetylcholine esterase (AChE) inhibitor therapy in addition to steroids. Such therapy, if successful, can also serve to reinforce the diagnosis. 
GUILLAIN-BARRE:
 
 o Important to consider here that the use of steroids as the primary treatment of Guillain-Barre is not typically considered effective.

Dosing Modification and Toxicity Management Guidelines for Immune-mediated, Infusion Related, and Non Immune-mediated Reactions (MEDI4736 Monotherapy or Combination therapy with Tremelimumab or Tremelimumab monotherapy)

	Grade of the Event (NCI CTCAE version 4.03)	Dose Modifications	Toxicity Management
			Patients requiring treatment should be started with IVIG and followed by plasmapheresis if not responsive to IVIG.
	Grade 3	Hold study drug/study regimen dose until resolution to \leq Grade 1 Permanently discontinue Study drug/study regimen if Grade 3 irAE does not resolve to \leq Grade 1 within 30 days or if there are signs of respiratory insufficiency or autonomic instability	
For severe or life threatening (Grade 3 or 4) events:
 
 - Discuss with study physician - Recommend hospitalization - Monitor symptoms and obtain neurological consult 
MYASTHENIA GRAVIS
 
 o Steroids may be successfully used to treat Myasthenia Gravis. It should typically be administered in a monitored setting under supervision of a consulting neurologist. o Patients unable to tolerate steroids may be candidates for treatment with plasmapheresis or IVIG. o If Myasthenia Gravis-like neurotoxicity present, consider starting acetylcholine esterase (AChE) inhibitor therapy in addition to steroids. Such therapy, if successful, can also serve to reinforce the diagnosis. 
GUILLAIN-BARRE:
 
Important to consider here that the use of steroids as the primary treatment of Guillain-Barre is not typically considered effective. Patients requiring treatment should be started with IVIG and followed by plasmapheresis if not responsive to IVIG

	Grade 4	Permanently discontinue study drug/study regimen	

Dosing Modification and Toxicity Management Guidelines for Immune-mediated, Infusion Related, and Non Immune-mediated Reactions (MEDI4736 Monotherapy or Combination therapy with Tremelimumab or Tremelimumab monotherapy)

Infusion-Related Reactions		
Severity Grade	Dose Modifications	Toxicity Management
Any Grade		
 - Management per institutional standard at the discretion of investigator - Monitor patients for signs and symptoms of infusion-related reactions (e.g., fever and/or shaking chills, flushing and/or itching, alterations in heart rate and blood pressure, dyspnea or chest discomfort, skin rashes etc.) and anaphylaxis (e.g., generalized urticaria, angioedema, wheezing, hypotension, tachycardia, etc.)
Grade 1	The infusion rate of study drug/study regimen may be decreased by 50% or temporarily interrupted until resolution of the event	For Grade 1 or Grade 2: 
 - Acetaminophen and/or antihistamines may be administered per institutional standard at the discretion of the investigator - Consider premedication per institutional standard prior to subsequent doses
Grade 2	The infusion rate of study drug/study regimen may be decreased 50% or temporarily interrupted until resolution of the event Subsequent infusions may be given at 50% of the initial infusion rate	
Grade 3/4	Permanently discontinue study drug/study regimen	For Grade 3 or 4: Manage severe infusion-related reactions per institutional standards (e.g., IM epinephrine, followed by IV diphenhydramine and ranitidine, and IV glucocorticoid)

Dosing Modification and Toxicity Management Guidelines for Immune-mediated, Infusion Related, and Non Immune-mediated Reactions (MEDI4736 Monotherapy or Combination therapy with Tremelimumab or Tremelimumab monotherapy)

Non-immune Mediated Reactions		
(Note: As applicable, for early phase studies, the following sentence may be added: “Any event greater than or equal to Grade 2, please discuss with Study Physician”		
CTC Grade/Severity	Dose Modification	Toxicity Management
Any Grade	Note: dose modifications are not required for adverse events not deemed to be related to study treatment (i.e. events due to underlying disease) or for laboratory abnormalities not deemed to be clinically significant.	Treat accordingly as per institutional standard
1	No dose adjustment	Treat accordingly as per institutional standard
2	Hold study drug/study regimen until resolution to ≤ Grade 1 or baseline	Treat accordingly as per institutional standard
3	Hold study drug/study regimen until resolution to ≤ Grade 1 or baseline For AEs that downgrade to ≤ Grade 2 within 7 days or resolve to ≤ Grade 1 or baseline within 14 days, resume study drug/study regimen administration at next scheduled dose. Otherwise, discontinue study drug/study regimen	Treat accordingly as per institutional standard
4	Discontinue Study drug/study regimen (Note for Grade 4 labs, decision to discontinue would be based on accompanying clinical signs/symptoms and as per Investigator’s clinical judgment and in consultation with the sponsor)	Treat accordingly as per institutional standard

Abbreviations:

AChE = acetylcholine esterase; ADA = American Dietetic Association; AE = adverse event; ALP = alkaline phosphatase; ALT = alanine aminotransferase; AST = aspartate aminotransferase; CT = computed tomography; GI = gastrointestinal; IDS=Infectious Disease Service; ILD = interstitial lung disease; IM = intramuscular; irAE = immune-related adverse event; IV = intravenous; NCI CTCAE = National Cancer Institute Common Terminology Criteria for Adverse Events; PO = by mouth; TNF = tumor necrosis factor; TSH = thyroid stimulating hormone; ULN = upper limit of normal.

Dosing Modification and Toxicity Management Guidelines for Immune-mediated, Infusion Related, and Non Immune-mediated Reactions (MEDI4736 Monotherapy or Combination therapy with Tremelimumab or Tremelimumab monotherapy)

ⁱ ASCO Educational Book 2015 “Managing Immune Checkpoint Blocking Antibody Side Effects” by Michael Postow MD

ⁱⁱ NCI CTCAE version 4.03

ⁱⁱⁱ ASCO Educational Book 2015 “Managing Immune Checkpoint Blocking Antibody Side Effects” by Michael Postow MD

^{iv} FDA Liver Guidance Document 2009 Guidance for Industry: Drug Induced Liver Injury – Premarketing Clinical Evaluation

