2. DEFINITIONS

Potential Hy's Law (PHL)

A Potential Hy's Law (PHL) case is defined as a study subject with an increase in serum Aspartate Aminotransferase (AST) or Alanine Aminotransferase (ALT) ≥ 3 x upper limit of normal (ULN) together with Total Bilirubin (TBL) ≥ 2 x ULN irrespective of serum Alkaline Phosphatase (ALP), at any point during the study following the start of study medication.

Hy's Law (HL)

A Hy's Law (HL) case is defined as a study subject with an increase in serum AST or ALT ≥ 3 x ULN together with TBL ≥ 2 x ULN, where no other reason can be found to explain the combination of increases, eg, elevated serum ALP indicating cholestasis, viral hepatitis, another drug.

For PHL and HL to be met the elevation in transaminases must precede or be coincident with (ie, on the same day) the elevation in TBL, but there is no specified timeframe within which the elevations in transaminases and TBL must occur.

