Immune-related Adverse Events (Overall Management For toxicities not noted below)	
Drug administration modifications of study drug/study regimen will be made to manage potential immune-related AEs based on severity of treatment-emergent toxicities graded per NCI CTCAE v4.03.
 
In addition to the criteria for permanent discontinuation of study drug/regimen based on CTC grade/severity (table below) , permanently discontinue study drug/study regimen for the following conditions:
 
 • Inability to reduce corticosteroid to a dose of ≤ 10 mg of prednisone per day (or equivalent) within 12 weeks after last dose of study drug/regimen • Recurrence of a previously experienced Grade 3 treatment-related AE following resumption of dosing. 	
It is recommended that management of irAEs follow the guidelines presented in this table
 
 - Patients should be thoroughly evaluated to rule out any alternative etiology (e.g., disease progression, concomitant medications, infections, etc.) - In the absence of a clear alternative etiology, all events should be considered potentially immune related. - Symptomatic and topical therapy should be considered for low-grade (Grade 1 or 2, unless otherwise specified) events - For persistent (greater than 3 to 5 days) low-grade (Grade 2) or severe (Grade ≥ 3) events promptly start prednisone PO 1-2mg/kg/day or IV equivalent - If symptoms recur or worsen during corticosteroid tapering 28 days of taper), increase the corticosteroid dose (prednisone dose [e.g. up to 2-4mg/kg/day or IV equivalent]) until stabilization or improvement of symptoms, then resume corticosteroid tapering at a slower rate (≥ 28 days of taper) - More potent immunosuppressives such as TNF inhibitors (e.g. infliximab) – (also refer to the individual sections of the immune related adverse event for specific type of immunosuppressive) should be considered for events not responding to systemic steroids. - Discontinuation of study drug is not mandated for Grade 3 / Grade 4 inflammatory reactions attributed to local tumour response (e.g. inflammatory reaction at sites of metastatic disease, lymph nodes etc.). Continuation of study drug in this situation should be based upon a benefit/risk analysis for that patient 		

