	
Grade 3 or 4 diarrhea
 
(Grade 3: stool frequency of ≥7 over baseline per day;
 
Grade 4: life threatening consequences)
	Permanently discontinue study drug/study regimen	
For Grade 3 or 4 diarrhea:
 
 - Promptly initiate empiric IV methylprednisolone 2 to 4 mg/kg/day or equivalent - Monitor stool frequency and volume and maintain hydration - Urgent GI consult and imaging and/or colonoscopy as appropriate - If still no improvement within 3-5 days of IV methylprednisolone 2 to 4mg/kg/day or equivalent, promptly start further immunosuppressives (e.g. infliximab at 5mg/kg once every 2 weeks). - Caution: Ensure GI consult to rule out bowel perforation and refer to infliximab label for general guidance before using infliximab. - Once improving, gradually taper steroids over ≥28 days and consider prophylactic antibiotics, antifungals and anti PCP treatment (please refer to current NCCN guidelines for treatment of cancer-related infections [Category 2B recommendation])

² ASCO Educational Book 2015 Michael Postow MD “Managing Immune Checkpoint Blocking Antibody Side Effects

Dosing Modification and Toxicity Management Guidelines for Immune-mediated, Infusion Related, and Non Immune-mediated Reactions (MEDI4736 Monotherapy or Combination therapy with Tremelimumab or Tremelimumab monotherapy)

	Grade of the Event (NCI CTCAE version 4.03)	Dose Modifications	Toxicity Management
Hepatitis (Elevated LFTs) Infliximab should not be used for management of Immune Related Hepatitis	Grade of Liver Function Test Elevation (CTCAE version 4.03) Any Grade		
 - Monitor and evaluate liver function test: AST, ALT, ALP and total bilirubin - Evaluate for alternative etiologies (e.g., viral hepatitis, disease progression, concomitant medications)
	Grade 1 (AST or ALT > ULN to 3 times ULN and/or TB > ULN to 1.5 times ULN)	No dose modification If it worsens, treat as Grade 2 event	For Grade 1 AST or ALT and/or TB elevation 
 - Continue LFT monitoring per protocol

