	Grade 2 (AST or ALT > 3 to 5 times ULN and/or TB >1.5-3.0 times ULN)	Hold Study drug/study regimen dose until grade 2 resolution to ≤ Grade 1 
 • If toxicity worsens then treat as Grade 3 or Grade 4 • If improves to baseline then treat at next scheduled treatment date Study drug/study regimen can be resumed at the next scheduled dose once event stabilizes to grade ≤1 and 5-7 days have passed after completion of steroid taper	For Grade 2 AST or ALT and or TB elevation : 
 - Regular and frequent checking of LFTs (e.g. every 1-2 days) until elevations of these are improving or resolved. - If no resolution to ≤ Grade 1 in 1-2 days, discuss with study physician. - If event is persistent (> 3-5 days) or worsens, promptly start prednisone 1-2mg/kg/day or IV equivalent. - If still no improvement within 3-5 days despite 1-2mg/kg/day of prednisone or IV equivalent, consider additional workup and prompt treatment with IV methylprednisolone 2-4mg/kg/day started. - If still no improvement within 3-5 days despite 2-4mg/kg/day of IV methylprednisolone, promptly start immunosuppressives (mycophenolate mofetil)³ . Discuss with study physician if mycophenolate mofetil is not available. Infliximab should NOT be used. - Once improving, gradually taper steroids over ≥28 days and consider prophylactic antibiotics, antifungals and anti PCP treatment (please refer to

³ ASCO Educational Book 2015 “Managing Immune Checkpoint Blocking Antibody Side Effects” , by Michael Postow MD

Dosing Modification and Toxicity Management Guidelines for Immune-mediated, Infusion Related, and Non Immune-mediated Reactions (MEDI4736 Monotherapy or Combination therapy with Tremelimumab or Tremelimumab monotherapy)

	Grade of the Event (NCI CTCAE version 4.03)	Dose Modifications	Toxicity Management
			current NCCN guidelines for treatment of cancer-related infections [Category 2B recommendation])

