	Grade 3 (AST or ALT >5-20 times ULN and/or TB > 3.0-10 times ULN	
For elevations in transaminases $\leq 8 \times$ ULN, or elevations in bilirubin $\leq 5 \times$ ULN
 
 -Hold study drug/study regimen dose until resolution to \leq Grade 1 or baseline -Resume study drug/study regimen administration at the next scheduled dose if elevations downgrade \leq Grade 1 or baseline within 14 days 
Permanently discontinue study drug/study regimen if the elevations do not downgrade to \leq Grade 1 or baseline within 14 days
 
For elevations in transaminases $> 8 \times$ ULN or elevations in bilirubin $> 5 \times$ ULN, discontinue study drug/study regimen
 
Permanently discontinue study drug/study regimen for any case meeting Hy's law criteria (ALT >
	
For Grade 3 or 4 AST or ALT and/or TB elevation:
 
 - Promptly initiate empiric IV methylprednisolone at 1 to 4 mg/kg/day or equivalent - If still no improvement within 3-5 days despite 1 to 4 mg/kg/day methylprednisolone IV or equivalent , promptly start treatment with immunosuppressive therapy (mycophenolate mofetil) Discuss with study physician if mycophenolate is not available. Infliximab should NOT be used. - Hepatology consult, abdominal workup, and imaging as appropriate. - Once improving, gradually taper steroids over ≥ 28 days and consider prophylactic antibiotics, antifungals and anti PCP treatment (please refer to current NCCN guidelines for treatment of cancer-related infections [Category 2B recommendation])

Dosing Modification and Toxicity Management Guidelines for Immune-mediated, Infusion Related, and Non Immune-mediated Reactions (MEDI4736 Monotherapy or Combination therapy with Tremelimumab or Tremelimumab monotherapy)

	Grade of the Event (NCI CTCAE version 4.03)	Dose Modifications	Toxicity Management
		3x ULN + bilirubin > 2x ULN without initial findings of cholestasis (i.e. elevated alkaline P04) and in the absence of any alternative cause ^{iv}	
	Grade 4 (AST or ALT > 20 times ULN and/or TB > 10 times ULN)	Permanently discontinue study drug/study regimen	

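### Appendix G's permanent Hy's Law stop names ALT only, so a bounded set of AST-led Hy's Law cases that recover has no explicit mandatory stop and may be re-dosed

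*Protocol*

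**What the plan says.** Four parts of the protocol bear on this.

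- **Appendix G, hepatitis, Grade 3 row.** It says "Permanently discontinue study drug/study regimen for any case meeting" Hy's Law criteria. The bracket that follows gives ALT above "3x ULN + bilirubin > 2x ULN without initial findings of cholestasis", and no alternative cause. AST does not appear. For transaminases up to 8x and bilirubin up to 5x ULN the same row has a hold rule: "Resume study drug/study regimen administration at the next scheduled dose if elevations downgrade" to Grade 1 or baseline within 14 days.
- **Appendix G, hepatitis, Grade 2 row.** The row covers "AST or ALT > 3 to 5 times ULN and/or TB >1.5-3.0 times ULN". Drug is held, and then "If improves to baseline then treat at next scheduled treatment date". The row makes no exception for Hy's Law.
- **Appendix E, Section 2.** A Hy's Law case "is defined as a study subject with an increase in serum AST or ALT" of at least 3x ULN together with bilirubin of at least 2x ULN and no other explanation. Section 5 of that appendix has such a case reported as an SAE, rated as related to the drug. The Hy's Law criteria in Section 6.4.3 also name both enzymes.
- **Section 5.8.** It makes Appendix G's discontinuation criteria mandatory. It also requires a stop for related events of Grade 3 or above, but exempts those that do not meet Appendix G's criteria. A further clause requires a stop when the investigator or the sponsor judges that an event rules out more dosing.

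**The concern.** Appendix E decides whether liver injury is a Hy's Law case caused by the drug. Appendix G decides whether the drug stops. The two use different enzyme criteria, and the narrower one governs dosing. Two patients with the same peak transaminase and bilirubin can then get opposite instructions, although Appendix E attributes both injuries to the drug. One must stop. The other may resume after recovery.

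What is at stake is patient safety: re-exposure after a liver injury that the protocol has classed as drug-induced. Hepatotoxicity is among the events of special interest in Section 5.5.3.1, and Section 12.4 provides for no data monitoring committee. The response and survival estimates are not affected.

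**Working it through.** There is no published figure to reproduce. The check applies the written rules to sets of values in multiples of ULN, written AST/ALT/bilirubin, assuming no other cause.

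**Rules used**

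- Appendix E Hy's Law: max(AST, ALT) ≥ 3 and bilirubin ≥ 2.
- Appendix G Hy's Law stop: ALT > 3 and bilirubin > 2.
- Other Appendix G hepatitis stops: any transaminase > 8; bilirubin > 5; Grade 4 (transaminase > 20 or bilirubin > 10); Grade 3 not back to Grade 1 or baseline in 14 days.
- Grade 2: transaminase > 3 to 5 and/or bilirubin > 1.5 to 3. Grade 3: transaminase > 5 to 20 and/or bilirubin > 3 to 10.

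**Results, assuming recovery (within 14 days if Grade 3)**

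| Values | Grade | Appendix E Hy's Law | Appendix G as written |
|---|---|---|---|
| 4/2/2.5 | 2 | yes | hold, may resume |
| 7/2/2.5 | 3 | yes | hold, may resume |
| 4/2/4 | 3 (by bilirubin) | yes | hold, may resume |
| 8/3/5 | 3 | yes | hold, may resume |
| 8.1/2/2.5 | 3 | yes | stop (> 8x) |
| 4/2/5.1 | 3 | yes | stop (> 5x) |
| 21/2.5/2.5 | 4 | yes | stop (Grade 4) |
| 2/7/2.5 | 3 | yes | stop (Hy's Law) |
| 2/4/2.5 | 2 | yes | meets the Hy's Law stop |

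The cleanest contrast is 7/2/2.5 with 2/7/2.5. Both are Grade 3 and differ only in which enzyme is raised.

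**Extent of the gap.** Take a grid in steps of 0.5 over AST 3-8 (11 values), ALT 1-3 (5) and bilirubin 2-5 (7). It has 11 × 5 × 7 = 385 points. All meet Appendix E and none meets an Appendix G stop. Grade 2 holds 5 × 5 × 3 = 75 of them and Grade 3 the other 310. The mirror grid, ALT 3.5-8 (10), AST 1-3 (5) and bilirubin 2.5-5 (6), has 10 × 5 × 6 = 300 points, and all meet both definitions. The grids test the logic and say nothing about how many patients would fall there.

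**Does another clause close the gap?**

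- Section 5.8's rule for related events of Grade 3 or above does not reach Grade 2. At Grade 3 it refers back to Appendix G's own criteria.
- Appendix G's two general stops are failure to reduce steroids within 12 weeks and "Recurrence of a previously experienced Grade 3 treatment-related AE following resumption of dosing". Neither covers a first Hy's Law episode that recovers.
- Appendix E prescribes notification, review and reporting, and gives no dosing instruction.
- The any-grade hepatitis line says "Monitor and evaluate liver function test: AST, ALT, ALP and total bilirubin" and asks for other causes to be considered. It has no dosing rule.

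**Timing.** Appendix E allows up to 3 weeks (21 days) from detection for the causality review. The Grade 3 resume rule works within 14 days. Its condition can therefore be met up to 21 − 14 = 7 days or more before the review is due.

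**Two lesser points.** The Hy's Law stop is printed only in the Grade 3 cell, although ALT above 3 to 5x with bilirubin above 2 to 3x is Grade 2. Its reference to any case, with Section 5.8, can be read to cover Grade 2, and the last table row relies on that reading. The difference between ≥ and > matters only at the exact threshold, such as ALT 3.0x with bilirubin 2.0x.

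**The case against.** The best reply is that the operative words are any case meeting Hy's Law criteria and that the bracket is loose shorthand. The stop carries an endnote to the 2009 FDA liver guidance, which Section 6.4.3 also cites for criteria naming both enzymes. Appendix G is a shared template that also covers tremelimumab regimens. A case agreed and reported under the term Hy's Law would naturally be taken to meet the criteria. This is a fair reading, but the bracket gives its own narrower definition and the line does not point to Appendix E. A site that follows the table literally would not stop.

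The safeguards are real. The study physician contacts the investigator once potential Hy's Law criteria are met. Senior sponsor physicians join the review within 3 weeks. Under Section 5.8 either the investigator or the sponsor can force a stop. Appendix B says the sponsor would not normally support a rechallenge. A Grade 2 case given steroids needs a taper of at least 28 days plus 5-7 more, so at least 33 days, which is past the 21-day review limit. These points make re-dosing less likely, but none imposes a stop. A Grade 2 case that settles without steroids has no such delay, and the Grade 3 resume line sets no taper condition. Section 5.5.3 describes Appendix G as an aid to judgement, but Section 5.8 makes its discontinuation criteria mandatory.

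A reader might infer that AST-led Hy's Law cases have no mandatory stop at all. The protocol does not support that, because the stops by magnitude, by Grade 4 and by failure to recover apply to AST as they do to ALT.

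**Conclusion.** The definitions conflict, and the conflict leaves a gap in a mandatory safety stop. The gap is limited to Hy's Law cases by Appendix E with AST about 3-8x, ALT at most 3x and bilirubin about 2-5x ULN that recover, within 14 days if Grade 3. There, continued treatment depends on judgement and review. Outside that region the drug already stops.

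This rests on reading the bracket literally and on other causes having been excluded. It does not show that the sponsor intends to re-dose such patients, and the review steps point the other way. The protocol gives no Hy's Law incidence, so the number affected cannot be computed; a few at most is assumed. The point should be fixed because the possible harm is serious and the change is small.

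**What to change.** Move the stop to the any-grade line of the Appendix G hepatitis section and reword it: 'At any grade, permanently discontinue for any case meeting Hy's Law criteria as defined in Appendix E (AST or ALT ≥3x ULN together with total bilirubin ≥2x ULN, with no other reason to explain the combination).' Add 'except Hy's Law cases' to the resume lines of the Grade 2 and Grade 3 rows.

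With the aligned definition, the open cases tested (for example 4.5/2.8/2.5, 6/2.5/2.5 and 7.5/2.9/4) all become permanent stops. The change also settles the Grade 2 placement and the threshold mismatch.

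The criteria in Section 6.4.3 and the procedures in Appendix E can stay as they are. The stop still requires that no other cause explains the values, so potential Hy's Law values explained by malignant disease and not significantly changed would still need no action under Appendix E, Section 7. The cost is one sentence moved and reworded, two short exceptions, and at most a few more patients stopping the drug. No new assessment is needed.
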